#### **Recommended Treatment Modifications for Immune-Mediated Adverse Reactions of YERVOY (Ipilimumab)**

Target/Organ System	Adverse Reaction	Treatment Modification
Endocrine	Symptomatic endocrinopathy	Withhold dose  Resume in patients with complete or partial resolution of adverse reactions (Grade 0 to 1) and who are receiving $< 7.5$ mg prednisone or equivalent per day.
	
 
• Symptomatic reactions lasting 6 weeks or longer
 
• Inability to reduce corticosteroid dose to <math>< 7.5</math> mg prednisone or equivalent per day
 
	Permanently discontinue
Ophthalmologic	Grade 2 through 4 reactions 
 
• not improving to Grade 1 within 2 weeks while receiving topical therapy or
 
• requiring systemic treatment
 
	Permanently discontinue
All Other	Grade 2	Withhold dose  Resume in patients with complete or partial resolution of adverse reactions (Grade 0 to 1) and who are receiving $< 7.5$ mg prednisone or equivalent per day.

	
 
• Grade 2 reactions lasting 6 weeks or longer
 
• Inability to reduce corticosteroid dose to 7.5 mg prednisone or equivalent per day
 
• Grade 3 or 4
 
	Permanently discontinue
--	---	-------------------------

The NCI Common Terminology Criteria for Adverse Events (CTCAE) Version 4.0 will be used to grade adverse events.

Patients enrolled in this study will be evaluated clinically and with standard laboratory tests before and at regular intervals during their participation in this study.

Patients will be evaluated for adverse events (all grades), serious adverse events, and adverse events requiring study drug interruption or discontinuation at each study visit for the duration of their participation in the study.

Due to the prolonged half-life associated with monoclonal antibodies, no dose reductions of either study agent are planned.

## 5.2 Dosing Delays

- In addition to the dose modifications in 6.1, any AE, laboratory abnormality or inter-current illness which, in the judgment of the investigator, warrants delaying the dose of study medication.

Subjects that have drug-related toxicities that meet the criteria for dose delay, should have both drugs (ipilimumab and Nivolumab) delayed until retreatment criteria are met.

Tumor assessments for all subjects should continue as per protocol even if dosing is delayed.

### 5.2.1 Criteria for Permanent Discontinuation of Nivolumab and Ipilimumab

- In addition to the treatment discontinuation parameters in 6.1, any treatment-related event that leads to delay in dosing lasting >12 weeks from ipilimumab dosing OR > 6 weeks from nivolumab dosing requires discontinuation, with the following exceptions:
  - Dosing delays within those time frames to allow for prolonged steroid tapers to manage drug-related adverse events are allowed.
  - Dosing delays lasting >12 weeks of ipilimumab or > 6 weeks of nivolumab from the previous dose that occur for non-drug-related reasons may be allowed.
- Any adverse event, laboratory abnormality, or intercurrent illness which, in the judgment of the Investigator, presents a substantial clinical risk to the participant with continued dosing.

Periodic study visits to assess safety and laboratory studies should also continue every 6 weeks or more frequently if clinically indicated during such dosing delays.

### 5.2.2 Criteria to Resume Nivolumab Dosing

- Drug-related pulmonary toxicity, diarrhea, or colitis must have resolved to baseline before treatment is resumed. Subjects with persistent Grade 1 pneumonitis after completion of a steroid taper over at least 1 month may be eligible for retreatment if discussed with and approved by the IND Sponsor.
- Drug-related endocrinopathies adequately controlled with only physiologic hormone replacement may resume treatment.
- Any Grade 3 drug-related laboratory abnormality (except lymphopenia, AST, ALT, or total bilirubin or asymptotic lipase or amylase). Any Grade  $\geq 3$  drug-related amylase or lipase abnormality that is not associated with symptoms or clinical manifestations of pancreatitis does not require dose delay. The IND Sponsor should be consulted prior to resuming nivolumab in such subjects.

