### 5. DOSING REDUCTIONS/DOSE DELAYS

#### 5.1 Dose Reductions

##### Recommended Dose Modifications for OPDIVO (Nivolumab)

Adverse Reaction	Severity	Dose Modification
Colitis	Grade 2 diarrhea or colitis	Withhold dose a
	Grade 3 diarrhea or colitis	Withhold dose a when administered as a single agent
	Grade 4 diarrhea or colitis	Permanently discontinue when administered with ipilimumab
Pneumonitis	Grade 2 pneumonitis	Withhold dose a
	Grade 3 or 4 pneumonitis	Permanently discontinue
Hepatitis	AST or ALT > 3 - 5 x ULN or total bilirubin > 1.5 - 3 x ULN	Withhold dose a
	AST or ALT > 5 ULN or total bilirubin > 3 x ULN	Permanently discontinue
Hypophysitis	Grade 2 or 3 hypophysitis	Withhold dose a
	Grade 4 hypophysitis	Permanently discontinue
Adrenal Insufficiency	Grade 2 adrenal insufficiency	Withhold dose a
	Grade 3 or 4 adrenal insufficiency	Permanently discontinue
Type 1 Diabetes Mellitus	Grade 3 hyperglycemia	Withhold dose a
	Grade 4 hyperglycemia	Permanently discontinue
Nephritis and Renal Dysfunction	Serum creatinine > 1.5 – 6 x ULN	Withhold dose a
	Serum creatinine > 6 x ULN	Permanently discontinue

Skin	Grade 3 rash or suspected Stevens-Johnson syndrome (SJS) or toxic epidermal necrolysis (TEN)	Withhold dose a
	Grade 4 rash or confirmed SJS or TEN	Permanently discontinue
Encephalitis	New-onset moderate or severe neurologic signs or symptoms	Withhold dose a
	Immune-mediated encephalitis	Permanently discontinue
Other	Other Grade 3 adverse reaction: First occurrence	Withhold dose a
	Recurrence of same Grade 3 adverse reactions	Permanently discontinue
	Life-threatening or Grade 4 adverse reaction	Permanently discontinue
	Grade 3 myocarditis	Permanently discontinue
	Requirement for $\geq 10$ mg per day prednisone or equivalent for $> 12$ weeks	Permanently discontinue
	Persistent Grade 2 or 3 adverse reactions lasting 12 weeks or longer	Permanently discontinue

\* Toxicity was graded per NCI CTCAE v4.

a Resume treatment when adverse reaction improves to Grade 0 or 1.

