### 5.2.3 Criteria to Resume Ipilimumab Dosing

- Subjects may resume treatment in the presence of Grade 2 fatigue.
- Subjects with baseline Grade 1 AST/ALT or total bilirubin who require dose delays for reasons other than a 2-grade shift in AST/ALT or total bilirubin may resume treatment in the presence of Grade 2 AST/ALT or total bilirubin.
- Drug-related endocrinopathies adequately controlled with only physiologic hormone replacement may resume treatment after consultation with the IND Sponsor.
- Treatment-related dose delay of ipilimumab which results in no ipilimumab dosing for  $> 12$  weeks requires ipilimumab discontinuation.
- Ipilimumab may not be resumed sooner than 6 weeks ( $\pm 5$  days) after the prior ipilimumab dose.
- In general, subjects who meet criteria to resume ipilimumab will also have met criteria to resume nivolumab, so it should be feasible to synchronize dosing of both drugs when resuming ipilimumab. In order to facilitate this, the dosing days of nivolumab and ipilimumab may be adjusted within the permitted  $\pm 5$  day window, as long as consecutive nivolumab doses are given at least 12 days apart.
- Any Grade 3 drug-related laboratory abnormality (except lymphopenia, AST, ALT, or total bilirubin or asymptotic lipase or amylase). Any Grade  $\geq 3$  drug-related amylase or lipase abnormality that is not associated with symptoms or clinical manifestations of pancreatitis does not require dose delay. The IND Sponsor should be consulted prior to resuming nivolumab in such subjects.

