# Hepatic Adverse Event Management Algorithm

Rule out non-inflammatory causes. If non-inflammatory cause, treat accordingly and continue I-O therapy. Consider imaging for obstruction.

Patients on IV steroids may be switched to an equivalent dose of oral corticosteroids (e.g. prednisone) at start of tapering or earlier, once sustained clinical improvement is observed. Lower bioavailability of oral corticosteroids should be taken into account when switching to the equivalent dose of oral corticosteroids.

[figure not shown]
\*I-O therapy may be delayed rather than discontinued if AST/ALT ≤ 8 x ULN or T.bili ≤ 5 x ULN.

\*\*The recommended starting dose for grade 4 hepatitis is 2 mg/kg/day methylprednisolone IV.

Updated 05-Jul-2016

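### Sections 5.1 and 5.2 and Appendix 2 contradict each other on some stop and resume instructions, and no passage says which text governs

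*Combined protocol and SAP*

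**What the plan says.** **Hepatic events.** The nivolumab table in Section 5.1 withholds for AST/ALT above 3 and up to 5 x ULN, or bilirubin above 1.5 and up to 3 x ULN. Above 5 x or 3 x ULN it discontinues permanently. The footnote to the hepatic algorithm in Appendix 2 reads: "I-O therapy may be delayed rather than discontinued if AST/ALT ≤ 8 x ULN or T.bili ≤ 5 x ULN".

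**Pulmonary toxicity, diarrhea and colitis.** Footnote a to the nivolumab table, which is attached to the Grade 2 pneumonitis and Grade 2 diarrhea or colitis rows among others, reads: "Resume treatment when adverse reaction improves to Grade 0 or 1". Section 5.2.2 says that these same toxicities, when drug-related, "must have resolved to baseline before treatment is resumed". It makes one allowance: persistent Grade 1 pneumonitis after a steroid taper of at least a month, with the IND Sponsor's approval.

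**Endocrine events.** In Section 5.1, "Grade 3 or 4 adrenal insufficiency" leads to permanent discontinuation of nivolumab, as does Grade 4 hypophysitis. Section 5.2.2 says: "Drug-related endocrinopathies adequately controlled with only physiologic hormone replacement may resume treatment". The ipilimumab counterpart in 5.2.3 adds a step: "Drug-related endocrinopathies adequately controlled with only physiologic hormone replacement may resume treatment after consultation with the IND Sponsor".

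**Delay limits and links.** Section 5.2.1 requires discontinuation when a treatment-related delay exceeds 12 weeks from ipilimumab dosing or 6 weeks from nivolumab dosing. Its first listed exception is: "Dosing delays within those time frames to allow for prolonged steroid tapers to manage drug-related adverse events are allowed". Sections 5.2 and 5.2.1 both present themselves as additions to rules in Section 6.1, which contains the adverse event definitions.

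**The concern.** An investigator with a subject in one of these situations can find two instructions, each part of the protocol, that lead to different actions. Neither action can be called a deviation with confidence, so monitoring has no fixed standard to check against. That is first a matter of patient safety.

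It also reaches the analysis. Objective 1.2.1 assesses tolerability partly through dose interruptions. Section 12.3.2 describes the dates and duration of delays. Section 12.4.3 tabulates adverse events leading to discontinuation and, for immune-mediated events, the action taken and dosing delays. If similar events are handled differently according to the page consulted, these summaries mix tolerability with the choice of page.

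**Working it through.** The point rests on comparing texts; the plan gives no figure for it.

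**1. Hepatic thresholds (nivolumab)**

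| Finding | Section 5.1 | Appendix 2 footnote |
|---|---|---|
| AST/ALT > 5 and ≤ 8 x ULN | permanent discontinuation | delay permitted |
| Bilirubin > 3 and ≤ 5 x ULN | permanent discontinuation | delay permitted |

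Within these bands one text ends treatment and the other allows it to be held. Labels do not settle the matter. Appendix 2 calls itself guidance, but the 5.1 tables are themselves headed as recommended modifications. Sections 5.4, 7.2.9 and 7.3.9 send investigators to Appendix 2.

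**2. Restarting nivolumab after Grade 2 diarrhea or colitis**

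| Baseline grade | Residual grade | 5.1 footnote a | 5.2.2 |
|---|---|---|---|
| 0 | 0 | restart | restart |
| 1 | 1 | restart | restart |
| 0 | 1 | restart | hold |

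The conflict is confined to the last row. For pneumonitis in that row, 5.2.2 allows a restart only after the taper and sponsor approval; footnote a asks for neither.

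**3. The steroid-taper exception in 5.2.1.** Let L be the limit (12 weeks for ipilimumab, 6 weeks for nivolumab). The stop rule applies to delays > L. The exception covers delays within the limit, that is ≤ L. No delay satisfies both, so the exception removes nothing from the stop rule.

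**4. Order of the rules.** If the references to 6.1 mean the 5.1 tables, the 5.1 stop rules come first and 5.2.2 concerns only subjects who were held. The endocrine sentences are then compatible. Read alone, 5.2.2 has no grade limit and could reach a Grade 3 or 4 adrenal insufficiency that 5.1 has already stopped. With the reference as printed, the text does not decide between the two.

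**5. Scale for one subject (illustration).** Assume nivolumab at weeks 0, 2, …, 102 under the two-year maximum in Section 4.6: 102/2 + 1 = 52 doses. Assume that a hepatic event in the conflict band causes the dose at week w to be missed, that the last dose was at w − 2, and that treatment resumes at w + 4, a six-week gap between doses that does not exceed the 5.2.1 limit. Doses still possible = (102 − (w + 4))/2 + 1.

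- w = 6: (102 − 10)/2 + 1 = 47
- w = 12: (102 − 16)/2 + 1 = 44
- w = 24: (102 − 28)/2 + 1 = 38

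Under permanent discontinuation the figure is 0. The counts are upper bounds, since they assume treatment continues to two years.

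**6. Design check.** With 20 subjects and at most 1 response at stage 1, then 56 subjects and at most 4 responses, exact binomial sums give early termination probability 0.736, expected size 20 + (1 − 0.736) × 36 ≈ 29.5 (29.51 unrounded), type I error 0.097 and type II error 0.199, as in Section 12.2. None of these inputs depends on the stop and resume rules.

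**The case against.** The strongest reply is that most of the rules can be followed together. Sections 5.2 and 5.2.1 add to earlier rules, and 6.1 is probably a numbering slip for 5.1: Section 4.10 likewise cites 6.3 for treatment beyond progression, which is in 5.3. On that reading a reader who infers a flat contradiction over adrenal insufficiency goes too far, because 5.2.2 would apply only to held subjects. This stands, except that the protocol does not state it.

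Three other strong readings also fail.

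- A reader might set "Subjects may resume treatment in the presence of Grade 2 fatigue" in 5.2.3 against the Grade 0 to 1 requirement of the ipilimumab table. It reads more naturally as a specific exception. The Grade 2 AST/ALT and bilirubin allowance is likewise limited to subjects with Grade 1 values at baseline whose delay had a cause other than a 2-grade shift in those tests.
- A reader might call the nivolumab limits of 6 weeks (5.2.1) and 12 weeks (5.1) opposite. The first counts time from dosing; the second counts how long a reaction persists or prednisone is needed. Both can apply, and whichever is reached first stops treatment.
- A reader might apply the 37% Grade 3-4 rate in Section 2.3.1 to this trial's sample size. That rate covers all related Grade 3-4 events in treatment-naïve NSCLC, not events on which the rules conflict.

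On colitis, a site that waits for baseline will normally satisfy both texts. True, but a site that restarts at residual Grade 1 follows footnote a and breaches 5.2.2. On the liver, the footnote's anchor lies in a figure that was not available for this review and may narrow its scope. Sponsor consultation, required for some resume decisions, reduces variation between sites but is not prescribed for the hepatic choice or for residual diarrhea.

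**Conclusion.** Two contradictions stand on the visible text: the hepatic thresholds, and the level of recovery needed to restart nivolumab after pulmonary toxicity, diarrhea or colitis. Two drafting faults stand beside them: an exception in 5.2.1 with no content, and references to 6.1 that leave the order of the rules uncertain, including for endocrinopathies that 5.1 stops permanently.

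The consequence is for patient safety and for descriptive secondary summaries with no test attached. A reader might infer that the primary analysis is compromised. The documents do not support that: the ORR population in 12.3.1 is fixed by receipt of one complete dose of nivolumab and ipilimumab, and the two-stage boundaries do not involve these rules. Objective 1.2.1 names interruptions and toxicities; discontinuations enter only through 12.4.3.

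The documents give no frequency for the conflicting situations in this population, so the overall effect cannot be sized. For an affected subject the choice of text can decide whether nivolumab continues at all. The hepatic finding assumes that the footnote applies to the bands shown.

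**What to change.** Amend the protocol in four places:

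1. Reconcile the hepatic thresholds in 5.1 with the Appendix 2 footnote, and footnote a of 5.1 with the recovery requirement in 5.2.2.
2. Add a sentence stating which text governs when 5.1, 5.2 and Appendix 2 differ, and whether the endocrine sentence in 5.2.2 can apply to events that 5.1 discontinues permanently.
3. Correct the references to 6.1 in 5.2 and 5.2.1.
4. Reword the first exception in 5.2.1 so that it states what it exempts.

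Which clinical rule to adopt is for the sponsor. The cost is amendment wording only: no change to sample size, endpoints or the primary analysis.

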### 5.2.3 Criteria to Resume Ipilimumab Dosing

- Subjects may resume treatment in the presence of Grade 2 fatigue.
- Subjects with baseline Grade 1 AST/ALT or total bilirubin who require dose delays for reasons other than a 2-grade shift in AST/ALT or total bilirubin may resume treatment in the presence of Grade 2 AST/ALT or total bilirubin.
- Drug-related endocrinopathies adequately controlled with only physiologic hormone replacement may resume treatment after consultation with the IND Sponsor.
- Treatment-related dose delay of ipilimumab which results in no ipilimumab dosing for  $> 12$  weeks requires ipilimumab discontinuation.
- Ipilimumab may not be resumed sooner than 6 weeks ( $\pm 5$  days) after the prior ipilimumab dose.
- In general, subjects who meet criteria to resume ipilimumab will also have met criteria to resume nivolumab, so it should be feasible to synchronize dosing of both drugs when resuming ipilimumab. In order to facilitate this, the dosing days of nivolumab and ipilimumab may be adjusted within the permitted  $\pm 5$  day window, as long as consecutive nivolumab doses are given at least 12 days apart.
- Any Grade 3 drug-related laboratory abnormality (except lymphopenia, AST, ALT, or total bilirubin or asymptotic lipase or amylase). Any Grade  $\geq 3$  drug-related amylase or lipase abnormality that is not associated with symptoms or clinical manifestations of pancreatitis does not require dose delay. The IND Sponsor should be consulted prior to resuming nivolumab in such subjects.

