## 6. ADVERSE EVENTS: LIST AND REPORTING REQUIREMENTS

This study will use the descriptions and grading scales found in the revised National Cancer Institute Common Terminology Criteria for Adverse Events (CTCAE) Version 4.0 for adverse event reporting that can be found at [http://ctep.cancer.gov/protocolDevelopment/electronic\\_applications/ctc.htm](http://ctep.cancer.gov/protocolDevelopment/electronic_applications/ctc.htm).

Information about all AEs, whether volunteered by the subject, discovered by investigator questioning, or detected through physical examination, laboratory test or other means, will be collected, recorded, and followed as appropriate.

All AEs and SAEs experienced by subjects will be collected and reported from the first dose of nivolumab, throughout the study, and will only be followed for 4 weeks unless related to the investigational agent. All SAEs will be collected for 100 days after the last dose of nivolumab. Subjects who have an ongoing AE related to the study procedures and/or medication(s) may continue to be periodically contacted by a member of the study staff until the event is resolved or determined to be irreversible by the investigator.

**Laboratory abnormalities:** Laboratory abnormalities present at the screening visit will be recorded as pre-treatment signs and symptoms. After study treatment administration, all grade 3 and 4 clinical laboratory results that represent an increase in severity from baseline will be reported as adverse events. A grade 1 or 2 clinical laboratory abnormality should be

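### Sections 5.2.2/5.2.3 and the Section 5.1 tables give different actions for a symptom-free Grade 3 or higher lipase or amylase rise, and no rule says which prevails

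*Combined protocol and SAP*

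**What the plan says.** Sections 5.2.2 (resuming nivolumab) and 5.2.3 (resuming ipilimumab) contain the same bullet. It says that any Grade 3 or higher "drug-related amylase or lipase abnormality that is not associated with symptoms or clinical manifestations of pancreatitis does not require dose delay". It then asks for the IND Sponsor to be consulted before nivolumab is resumed, and this wording appears in the ipilimumab section too.

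Section 5.1 has two tables.

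- The nivolumab table has general rows under Other. For "Other Grade 3 adverse reaction: First occurrence" the action is to withhold, resuming at Grade 0 or 1. For "Recurrence of same Grade 3 adverse reactions" and for "Life-threatening or Grade 4 adverse reaction" it is permanent discontinuation.
- The ipilimumab table is titled as covering immune-mediated reactions. Its All Other rows require permanent discontinuation at Grade 3 or 4.

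Neither table mentions lipase or amylase.

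Section 5.2 opens "In addition to the dose modifications in 6.1" and Section 5.2.1 opens "In addition to the treatment discontinuation parameters in 6.1". Section 6.1 contains adverse event definitions, so 5.1 must be meant. Section 5.2 adds that subjects whose drug-related toxicity meets the delay criteria "should have both drugs (ipilimumab and Nivolumab) delayed until retreatment criteria are met". Section 6 states that, once treatment has started, "all grade 3 and 4 clinical laboratory results that represent an increase in severity from baseline will be reported as adverse events".

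**The concern.** A site that receives a high lipase value in a subject who feels well finds two instructions. The resumption sections say dosing need not be delayed. The nivolumab table says to hold, or to stop for good. The protocol does not say which governs.

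The situation is likely to arise. Section 2.3.1 lists increased lipase first among the most common Grade 3-4 related events in the cited lung cancer study, one arm of which used this trial's ipilimumab dose and interval. Note f of the study calendar includes lipase and amylase in the laboratory tests before each dose.

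Two things are at stake. One is dosing: a subject without clinical harm may or may not keep study drug, depending on the section consulted. The other is the tolerability result. Objective 1.2.1 quantifies dose interruptions, and 12.4.3 tabulates adverse events leading to discontinuation. If sites follow different sections, the same event is a discontinuation, a delay or neither, and those summaries mix drug tolerability with choice of rule.

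**Working it through.** The plan states no figure on this point, so the check compares the texts.

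**Step 1. Is a laboratory-only value within the nivolumab Other rows?** Section 6 reports worsening Grade 3-4 laboratory results as adverse events, and the value described in 5.2.2 and 5.2.3 is drug-related by definition. The Other rows are not limited to immune-mediated or symptomatic events. So yes.

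**Step 2. Is it within the ipilimumab All Other rows?** This is open. The table's title limits it to immune-mediated reactions. Section 6.6.1 defines non-endocrine immune-mediated events as listed events treated with immunosuppression, and Table 2 has no lipase, amylase or pancreatitis term. But the 5.1 table does not refer to that definition, and its All Other label is broad.

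**Step 3. Apply each rule to the same symptom-free, drug-related rise.**

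| Event | 5.2.2 and 5.2.3 | 5.1 nivolumab, Other | 5.1 ipilimumab, All Other (if it applies) |
|---|---|---|---|
| Grade 3, first time | No delay | Hold until Grade 0-1 | Permanent stop |
| Grade 3, recurrent | No delay | Permanent stop | Permanent stop |
| Grade 4 | No delay | Permanent stop | Permanent stop |

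The nivolumab column differs from 5.2.2 in every row. The ipilimumab column differs from 5.2.3 in every row, but only on one answer to Step 2.

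**Step 4. Does any text settle precedence?** No. The opening phrases of 5.2 and 5.2.1 make their own content additional to the tables. They do not rank the tables against 5.2.2 and 5.2.3.

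**Step 5. What size can be given?** Treatment lasts up to 2 years (4.6) with nivolumab every 2 weeks: 104 / 2 = 52 doses at most, each with a scheduled lipase value. For the number of subjects affected, the only figure is the 37% with any Grade 3-4 related event on the every-6-week ipilimumab schedule in 2.3.1. Assuming that rate carried over from lung cancer, 0.37 × 56 = 20.7 subjects would have an event of any type. The lipase share of this is not given.

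**Step 6. Endocrine rows.** The ipilimumab Endocrine rows allow resumption only below 7.5 mg prednisone equivalent per day and stop the drug if that dose cannot be reached. Section 4.2.2.5 permits adrenal replacement up to 10 mg, and 5.2.3 lets subjects controlled on physiologic replacement resume after sponsor consultation. The rows do not say whether replacement counts toward the limit, so the doubt mainly concerns doses from 7.5 to 10 mg. The nivolumab hypophysitis and adrenal insufficiency rows likewise omit the replacement provision of 5.2.2.

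**The case against.** The best defence is that the specific rule governs the general one. Sections 5.2.2 and 5.2.3 are the only dosing rules that name lipase and amylase, both 5.1 tables are headed as recommendations, and the sponsor consultation gives sites a way to resolve doubt. This is a natural reading and probably the intended one. But the protocol does not state it, and the table rows are worded as actions. The consultation sentence is itself unclear, since it concerns resuming a drug that was never delayed.

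Three stronger conclusions are tempting, and the documents do not support them.

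- A reader might infer that one high value certainly costs the subject ipilimumab. That requires the immune-mediated table to cover an untreated, symptom-free enzyme rise, which is only one reading. On the firmer nivolumab conflict, a first Grade 3 value brings a hold; a permanent stop under these rows needs recurrence or Grade 4.
- A reader might infer that the exception can never operate because 5.1 acts first and 5.2 then delays both drugs. But the both-drugs sentence covers only toxicities that meet the delay criteria, and 5.2.2 and 5.2.3 say this one does not require delay.
- A reader might infer a loss of response rate or power. Any such figure needs an assumed lipase rate, an assumed share losing drug before responding, and an assumed drop in their response. The documents supply none of these.

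The reporting worry is also partly met. Section 12.4.3 tabulates discontinuations by preferred term and 12.3.2 describes dates and duration of delays, so a lipase stop would be visible. What remains is that its presence or absence may reflect the section followed.

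**Conclusion.** The inconsistency is real and should be corrected. It is firm for nivolumab. For ipilimumab it depends on whether an isolated enzyme rise is treated as an immune-mediated reaction. Its consequence is that one symptom-free value may bring no action, a hold or a permanent stop, with matching differences in the tolerability counts.

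The number of subjects affected cannot be estimated from the documents. The two-stage response-rate design is not called into question, and no change in its power or type I error is claimed. The endocrine gap is a minor clarification. The conclusion rests on the dosing text alone and on reading 6.1 in 5.2 and 5.2.1 as a slip for 5.1.

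**What to change.** 1. In 5.1, add to the nivolumab Other rows for first Grade 3, recurrent Grade 3 and Grade 4, and to the ipilimumab All Other row for Grade 3 or 4: *except a drug-related amylase or lipase rise with no symptoms or clinical signs of pancreatitis, which follows 5.2.2 and 5.2.3*. Symptomatic cases keep the 5.1 action.
2. In 5.2.2 and 5.2.3, replace the instruction to consult before resuming nivolumab with consultation of the IND Sponsor about continuing study drug.
3. Correct 6.1 to 5.1 in 5.2 and 5.2.1.
4. State that the 7.5 mg limit in the ipilimumab Endocrine rows refers to steroid given to treat the reaction, and that endocrinopathies controlled on physiologic replacement follow 5.2.2 and 5.2.3. Put the same cross-reference in the nivolumab hypophysitis and adrenal insufficiency withhold rows.

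The cost is a few phrases and no new procedures. The downside is that some subjects with symptom-free Grade 3-4 enzyme rises stay on drug, followed by the pre-dose draws already scheduled. Keeping the exception at Grade 4 is a clinical judgment that the sponsor should confirm when making the change.
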